Principal Investigator: [name]
Protocol Title: Improve Glaucoma Medication Adherence
Version#6 01/09/2018

Purpose

The purpose of this study is to improve glaucoma medication adherence in Veterans with medically-treated glaucoma. The study design is a single-site randomized controlled trial.

Background and Significance

Glaucoma is the leading cause of irreversible blindness worldwide^{1,2} and the leading cause of blindness in African Americans.³ The number of Americans with glaucoma is projected to increase by 50% over the next 15 years.⁴ Despite advancements in the diagnosis and treatment of glaucoma, no cure exists. The only intervention that has been proven to reduce the risk of progressive loss of vision from glaucoma is lowering the intraocular pressure. Although surgery and laser treatment may be used to reduce intraocular pressure, the most common treatment for glaucoma is the prescription of topical eye drops.⁵

Glaucoma eye drops are prescribed to be taken daily, often multiple times per day, indefinitely. As with many other daily therapies for chronic, asymptomatic disease, patient adherence to the prescribed glaucoma regimen is often poor.^{6,7} Patients with glaucoma who are poorly adherent to the prescribed medication regimen are more likely to experience progressive visual field loss than patients who are more adherent.⁸ Factors associated with poor glaucoma medication adherence include advanced age,⁹ limited health literacy skills,¹⁰ and disabilities from comorbid conditions that make self-administration of eye drop difficult, such as arthritis.¹¹

The approach to assess and address glaucoma medication adherence is guided by the Health Decision Model (HDM). The HDM suggests that adherence with the prescribed glaucoma eye drop regimen is dependent on patient experiences, patient preferences, social interactions, knowledge, attitudes and beliefs (Figure 1). The educational components of the intervention address the potential for irreversible blindness from glaucoma and increase understanding that eye drops reduce the risk of blindness. The self-reported adherence and self-efficacy surveys create the personalized response component of the intervention, which incorporates patient experience and preferences regarding most convenient dosing regimen. In addition, personalized responses are used to increase participants' self-efficacy with eye drop use. For example, participants who describe low self-efficacy with the physical task of administering the drop are taught simple tricks such as steadying the hand on the forehead, or prescribed eye drop aids to help with squeezing or aiming the bottle. We have found in our prior work that glaucoma patients expressing poor self-efficacy regarding ability to take their drops as prescribed are less adherent in the following months according to an electronic monitor¹ so the screening questions we tested in our preliminary work target self-efficacy.

This study will expand upon previous work and incorporate the most current evidence-based strategies into the design. The authors of a 2009 Cochrane review concluded that although there were too few studies of glaucoma medication adherence of high quality to make firm recommendations, interventions that include glaucoma education and individualized care planning are most successful.⁴⁵ Boland and colleagues have shown that mnemonic aides in the form of automated text or voicemail messaging can improve adherence, at least in the short-term.⁴ We know, however, that even experienced drop-users often cannot successfully administer a drop into the eye,² and daily reminders will not alleviate this barrier to adherence.

Accordingly, a more comprehensive approach is needed to improve glaucoma self-management.

The long-term goal of this research program is to reduce glaucoma-related blindness in Veterans. The objective of this project is to test an intervention to improve medication adherence. The proposed intervention is novel in that it was developed through a prior pilot study with input from Veterans with glaucoma and with a multidisciplinary team that includes local and national operations partners. This collaborative approach and careful attention to cost will facilitate implementation of the program should the intervention prove effective. The screening and outcomes measures have also been studied in the Durham VA Eye Clinic as part of the preliminary studies leading to this proposal.

Design

The proposed study is a randomized controlled trial of an educational intervention to improve glaucoma medication adherence. Participants will be Veterans who are patients of the Durham VA Eye Clinic with medically-treated glaucoma and their companions (family or friend) if a companion is available (we have been approved for a Waiver of Informed Consent Documentation for companions). Participants will be randomized to receive either a general eye health educational session (control arm) or an educational intervention developed to improve glaucoma medication adherence (intervention arm). All participants will be provided with a "smart bottle" (AdhereTech, NYC) to house one of their glaucoma medications. The smart bottle records the date and time that the bottle is opened. For participants in the intervention arm only, a reminder through AdhereTech will be activated. Participants randomized to the intervention will meet with the interventionist approximately 4 weeks following the enrollment visit. The intervention will be delivered one-on-one, in a private room at the Durham VA. Companions, if applicable, will accompany the Veteran in the intervention. Drop administration instruction will be directed toward the veteran participant or if applicable towards the companion. Veterans randomized to the control arm will be scheduled for a session with the interventionist approximately 4 weeks after the enrollment visit. The control visit will include review of a Powerpoint presentation on general eye health, including but not specific to glaucoma. The presentation will be delivered one-on-one, in a private room at the Durham VA. Companions, if applicable, will accompany the Veteran in the presentation. Both the intervention and the control session will last approximately 30-60 minutes. Participants in the control arm will receive an electronic medication monitor but the reminder function will not be activated. Participants will be brought in for a 6-month follow up visit and the 12 month follow up will be conducted over the telephone.

Outcomes:

Specific Aim 1. Evaluate the impact of an intervention to improve glaucoma medication adherence among Veterans at 6-month follow up.

Hypothesis 1: Veterans randomized to the intervention will have a greater proportion of prescribed glaucoma medication doses taken as measured by the electronic medication monitor in the 6 months following the intervention compared to Veterans randomized to the control arm.

The primary outcome for hypothesis 1A is the proportion of prescribed doses taken according to the electronic monitor. Participants in both arms will receive the electronic monitor or "smart bottle," which wirelessly transmits the date and time of opening of the smart bottle to the study team. From these medication events, the proportion of prescribed doses will be derived, defined as the ratio of the number of times the smart bottle was opened to the required number of doses prescribed according to the medical record over the period of time that the bottle is in use. For example, if a participant is advised to take his or her glaucoma drop twice a day for the 180 days that the bottle is in use and the smart bottle reveals 135 openings over the same time period, the proportion of prescribed doses taken is 37.5%.

Specific Aim 2. Evaluate the impact of the intervention on intensification of glaucoma therapy among Veterans at 12-months post randomization.

Hypothesis 2: The proportion of Veterans in the intervention arm that are prescribed more intensive glaucoma therapy, defined as addition of adjuvant glaucoma medication or recommendation for laser or glaucoma surgery will be less than the proportion of Veterans in the control arm who are prescribed more intensive glaucoma therapy in the 12 months following the intervention.

Baseline data collection will include cataloging the current glaucoma medication regimen prescribed to the participant. Chart abstractions will be performed at approximately 12 months following the randomization and intensification of glaucoma therapy will be defined as either 1) the addition of another glaucoma medication to the baseline regimen, 2) recommendation for glaucoma laser treatment, or 3) recommendation for glaucoma surgery in the 12 months following randomization. We will collect these data at approximately 12 months because the Metrics study suggested that 55% of participants in the control arm will have intensification of therapy within one year.

Specific Aim 3. Evaluate the incremental cost-effectiveness and budget and workflow impacts of the intervention compared to usual care.

Hypothesis 3: The intervention will be cost-effectiveness for the following ratios: 1) cost per percentage improvement in medication adherence; 2) cost per blindness averted; and 3) cost per quality-adjusted-life years saved.

A direct measurement approach will be used to estimate per-patient intervention and control arm costs. Glaucoma-related health care utilization costs will be derived from VA administrative datasets. The cost estimates will be combined with observed improvement in medication adherence and reduction in escalation in therapy to estimate the first two incremental cost effectiveness ratios. Simulation using Markov modeling will be used to estimate the incremental cost per blindness averted and quality-adjusted life years (QALYs) gained. Cost estimates and labor time data collected will be combined with glaucoma prevalence rates among Veterans to estimate overall budget and workload impacts to the VA healthcare system.

Risk/Benefit Assessment

The intervention is educational in nature and does not impose physical risks to participants. The primary risks to participants are loss of time and confidentiality. Participants' time was considered as an important factor in designing an intervention which is efficient yet hopefully effective. Actions taken to mitigate the risk of loss of confidentiality are addressed in the sections "Privacy and Confidentiality" and "Information Security." If, in the course of the study, any information becomes available that might influence the course of clinical care of the participant, this information will be communicated directly to the treating provider. The study offers no definitive benefit to participants but the knowledge gained may lead to improvements in the management of glaucoma for future patients.

Selection of Subjects

We will screen individuals until we meet the desired sample size of randomizing 200 Veterans and enroll up to 200 of their companions (family or friend) if a companion is available. Enrollment of a companion will not be required for otherwise eligible Veterans to be included in the study.

Inclusion criteria for patients at datapull:

- 1) Diagnosis of open angle glaucoma [primary open angle glaucoma, pigment dispersion glaucoma, pseudoexfoliation glaucoma, combined mechanism glaucoma, low tension glaucoma] recorded in the medical record,
- 2) Prescribed glaucoma eye drops,
- 3) Visual field performed within the last 9 months. As visual field testing is standard care glaucoma and we wish to establish baseline glaucoma severity, we will require that subjects have a visual field test documented in the chart within 18months of enrollment.

Exclusion criteria for patients:

- 1) Intraocular surgery in the past 3 months or anticipated in the next 3 months [as prescribed drops may change frequently in the perioperative period],
- 2) Active uveitis or eye infection [as medication regimen may vary from day to day],
- 3) Visual acuity less than 20/70 in the better-seeing eye, because Veterans with low vision may not be able to complete the vision-dependent tasks required for study completion.
- 4) Lacks proficiency in English,
- 5) Lacks either a cell phone or landline phone

Exclusion criteria for patients At Screener:

“How confident are you that you always remember to use your glaucoma medications? (not at all confident, somewhat confident, very confident)” and “In the past 4 weeks, did you ever forget to take your medicine?” Veterans who respond both “very confident” and “no”, respectively, will be excluded.

Inclusion criteria for companions at screener:

- 1) Willing to participate in assisting the patient with glaucoma drops and
- 2) Willing to accompany the patient to the intervention visit for participants in the intervention arm or eye health education visit for participants in the control arm.

Exclusion criteria for companions: Unable or unwilling to attend baseline visit and intervention or control arm educational session with patient participant.

Exclusion criteria for patients or companions:

- 1) Lacks proficiency in English,
- 2) Lacks either a cell phone or landline phone.

Exclusion criteria for patients post randomization:

1. Decision by patient and provider to cease glaucoma medication use
2. Change in functional status such that the drops are no longer administered by the patient or the companion (such as nursing home care)

Subject Recruitment

Recruitment and Enrollment Process: We will use a recruitment strategy that was very efficient in our pilot studies. Potential participants will be identified by a data pull of Veterans with upcoming appointments at the DVAMC meeting inclusion/exclusion criteria. The medical records of potential participants identified by the data pull will be reviewed in detail to confirm eligibility based on the remaining inclusion/exclusion criteria. Potential participants confirmed to be eligible will be mailed a letter providing study information and a phone number to call to opt out of further contact regarding the study. Veterans who were mailed letters and did not opt out will be called by the study coordinator to discuss potential participation. If the Veteran is interested, screening questions will be asked to identify potential participants most likely to be poorly adherent to their prescribed glaucoma medication regimen. Veterans who screen positive for poor adherence and are interested in participation will be scheduled for an

appointment along with a companion if a companion is involved in his or her glaucoma management. Written informed consent and HIPAA authorization from the Veteran will be obtained at that time.

Recruitment Targets and Feasibility: We plan to randomize 200 Veterans (and enroll up to 200 companions if appropriate) over 24 months. Our pilot study identified 1533 Veterans meeting preliminary inclusion/exclusion criteria. In our pilot study, we used the proposed recruitment strategy and enrolled 31 Veterans over 3 months. In the proposed study, we will recruit 4-5 days/week, which greatly expands our ability to enroll and comfortably achieve our recruitment goal.

Consent Process

Potential participants who are eligible and express interest in the study after the screener phone call will meet in person with a member of the research team in a private room in the Durham VAMC or Hillandale clinic. The study will be described in detail and all questions answered. If the patient chooses to participate they will sign and date the informed consent and HIPAA forms. The signed informed consent and HIPAA documents safeguarded under lock and key at locations managed by the Durham VA Medical Center HSR&D: [name]. While we will go through a consent process for companions, we were granted a Waiver of Informed Consent Documentation and a Waiver of HIPAA Authorization for the companion.

Study Interventions

[figure not shown]
The variables and data collection schedule are presented below (Table 1).

Baseline Data Collection: To reduce travel burden (and increase recruitment), we will strive to administer baseline surveys following informed consent on the day of a Veteran's scheduled appointment at the Durham VAMC or Hillandale clinic. However, we will make multiple dates and times available to the participants; and whenever possible, we will coordinate the baseline with a regularly scheduled appointment.

Randomization and Stratification: Participants will be randomized at the first informational session in a 1:1 allocation to the intervention or to the control arm. Randomization will be stratified according to if a companion is enrolled in the study with the participant. We anticipate 20% of participants will include a companion.⁶⁰ Randomization will also be stratified according to whether the glaucoma medication housed by the AdhereTech bottle is prescribed to be take once daily or more than once daily. Randomization status will be disclosed to the participant at the time of the intervention or control arm eye health education visit. Neither participants nor staff can be masked to randomization status.

Retention: To minimize participant burden and maximize their retention, screening is conducted over the phone. We will make multiple dates and times available to the participants; whenever possible, we will coordinate the baseline, education and information session and 6-month study visit with a regularly scheduled appointment. Our study staff will call participants prior to the intervention visit to confirm availability and remind them of the study appointment. In order to maximize retention during the follow-up phase of the study, study staff will contact participants by telephone as needed and ask about any problems using the smart bottle.

Study Flow:

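### The primary outcome counts every smart-bottle opening with no daily cap, so surplus openings offset missed doses; time in use is also undefined after abandonment or device failure

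*Combined protocol and SAP*

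**What the plan says.** All references are to the combined protocol and SAP.

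- **Numerator and denominator.** Outcomes, Specific Aim 1, defines the outcome as "the ratio of the number of times the smart bottle was opened to the required number of doses prescribed according to the medical record". The worked example uses only a total count of openings. Neither this section nor Data Analysis and Statistical Considerations, Specific Aim 1, has a daily cap, a 100% ceiling or a rule for repeat openings.
- **Period.** The same definition counts "over the period of time that the bottle is in use", and the example has a participant prescribed drops "for the 180 days that the bottle is in use". Hypothesis 1 instead refers to doses taken "in the 6 months following the intervention compared to Veterans randomized to the control arm", and the analysis section uses that 6-month window.
- **Analysis.** The ratio is Y in a linear model adjusted for dosing frequency and companion. The treatment effect is beta1, a difference in means.
- **Difference between arms.** The Design section states: "For participants in the intervention arm only, a reminder through AdhereTech will be activated". Under Intervention Arm Content, items 4 and 5 give that arm instillation coaching with individual feedback and reminders tailored to reported barriers.
- **Device problems.** Under Retention, staff telephone as needed and ask about trouble with the bottle. No counting rule follows from the answer.

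**The concern.** The ratio is described as a proportion of prescribed doses taken, but it adds up openings without asking when they happened. A second opening on Tuesday replaces a missed dose on Wednesday. Two people with the same total can therefore have covered very different shares of their doses.

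This matters for the trial comparison only if surplus openings differ between arms. Reminders and instillation coaching go to one arm only, and either could raise or lower the number of surplus openings, so equality cannot be taken for granted. The result also reaches beyond Aim 1. Under Data Analysis for Cost, the first cost-effectiveness ratio uses the adherence improvement and is calculated only if the main outcome differs significantly.

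The second, smaller issue is what *in use* means once a participant has permanently stopped using the bottle or the device has failed. Those days can be dropped or counted as missed. The text does not choose, and it does not reconcile *in use* with the 6-month window.

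**Working it through.** **Inputs from the documents:** 135 openings, two doses a day, 180 days, result 37.5% (Outcomes, Specific Aim 1); 200 Veterans randomized 1:1. **Assumed:** every opening pattern, rate, stopping share, analysed sample size and SD below.

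**1. The plan's figure.** 135 / (2 × 180) = 135/360 = 37.5%. It reproduces, and the example is not an error.

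**2. Same total, different coverage.** If openings never exceed two a day, a daily cap changes nothing: 37.5%. If they were three on each of 45 days (3 × 45 = 135), the uncapped score is still 37.5%, but the capped score is (2 × 45)/360 = 90/360 = 25.0%.

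**3. Once-daily patterns over 180 days.**
- 120 days with one opening, 30 with two, 30 with none: (120 + 60)/180 = 100% uncapped; 150/180 = 83.3% capped.
- 150 days with one opening, 30 with two: (150 + 60)/180 = 116.7% uncapped; 180/180 = 100% capped.

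**4. Arm level.** Let p be the share of doses taken and q the chance that a taken dose is followed by one surplus opening.
- Uncapped mean: p(1 + q).
- Capped, once daily: p.
- Capped, twice daily with independent doses: both taken counts 2, exactly one taken counts 1 + q on average, so the mean is [2p² + 2p(1 − p)(1 + q)]/2 = p + p(1 − p)q.

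With p = 0.70 in both arms, a between-arm difference dq in q shifts beta1 by 0.70 dq uncapped, 0 capped once daily, and 0.70 × 0.30 × dq = 0.21 dq capped twice daily:

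| dq (percentage points) | Uncapped | Capped, once daily | Capped, twice daily |
|---|---|---|---|
| 0 | 0 | 0 | 0 |
| 5 | 3.5 | 0 | 1.05 (about 1.1) |
| 10 | 7.0 | 0 | 2.1 |

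The sign depends on which arm has more surplus openings.

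**5. Time in use.**
- Once daily, perfect use, abandoned at day 90: 90/90 = 100% if *in use* ends at the last opening; 90/180 = 50% over 180 days.
- Device failure at day 120 after 90% use: 108/120 = 90% or 108/180 = 60%.
- Arm level, 70% use while active, abandonment at day 90 by 20% of controls and 10% of the intervention arm: the arms differ by 0 on the first reading. Over 180 days they differ by 0.70 × 0.5 × 0.10 = 3.5 points. Equal abandonment gives 0, and swapping the shares gives −3.5.

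**6. Scale.** The documents give no SD or power. With 80 to 100 analysed per arm and an SD of 20 to 30 points (assumed), the difference detectable with 80% power is 2.802 × SD × √(2/n): 7.9 points (n = 100, SD 20) to 13.3 points (n = 80, SD 30).

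**The case against.** **The rule is explicit and reproducible, and the Background says the outcome measures were studied in this clinic.** True. A capped sensitivity analysis would also expose surplus openings without redefining the outcome. But Hypothesis 1 is about doses taken, so the primary comparison should carry that meaning.

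**A cap brings its own error.** This stands. A nightly dose opened alternately at 23:30 and 00:30 scores 50% if days are cut at midnight and 100% if cut at 03:00. The boundary must be stated in advance.

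**Nothing in the documents reports surplus openings.** This also stands. The reminder is described as an alert to missed doses, which would prompt a first opening rather than a second. Recruitment is aimed at poor adherers: "screening questions will be asked to identify potential participants most likely to be poorly adherent to their prescribed glaucoma medication regimen". That makes scores above 100% less likely, but does not stop a surplus hiding a missed dose.

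**Return timing.** A reader might infer that a bottle returned before or after day 180 has no counting rule. The documents do not support that. Openings and doses are both counted over the time in use, so a return at day 150 after 80% use scores 120/150 = 80%. What remains is a mismatch with the 6-month wording, and the 180-day example and six intervals of 30 days lean towards a fixed window.

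**Post-randomization exclusions.** A reader might also see a counting gap in "Decision by patient and provider to cease glaucoma medication use" and "Change in functional status such that the drops are no longer administered by the patient or the companion". These are listed as exclusions, so they raise the question of who is analysed, which is a separate matter.

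**Abandonment would be noticed.** The longitudinal model and the telephone contact make that likelier, but neither supplies a rule for the primary outcome.

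**Conclusion.** The point holds. The stated formula has no daily cap, so surplus openings offset missed doses and the outcome can exceed 100%. On the assumptions shown (70% of doses taken, surplus rates differing by 5 to 10 percentage points between arms), beta1 moves by 3.5 to 7.0 points, which is not trivial beside an assumed detectable difference of 7.9 to 13.3. A cap reduces this to 0 for once-daily drops and 1.1 to 2.1 points for twice-daily drops. The secondary gap is confined to abandonment and device failure, where opposite readings can halve an individual score.

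A reader might go further and infer that the outcome favours the intervention arm. The documents do not support this: they give no surplus or abandonment rates, equal rates cancel, and the one-arm components could push either way. This should be fixed, but it does not invalidate the trial.

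**What to change.** Before arm-level data are examined, give one definition in both the Outcomes and Data Analysis sections for Specific Aim 1:

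- **Ratio:** the sum over dosing days of min(openings, doses prescribed that day), divided by the doses prescribed from bottle issue to day 180, or to bottle return if sooner.
- **Day boundary:** one pre-stated clock hour, away from usual dosing times.
- **Silent days:** days without openings count as missed, including after abandonment while the participant is still in the study.
- **Removed from numerator and denominator, by the same rule in both arms:** documented device failure, and time after death or withdrawal from the study.
- **Post-randomization exclusions:** left to the definition of the analysis population.
- **Sensitivity analyses:** (1) the uncapped ratio; (2) the ratio ending at the last opening.

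The cost is small. Each opening is already transmitted with date and time, and the bottle is already brought back at the 6-month visit. The change needs aligned wording, a few lines of code and a simple device-failure log.

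Three limits remain. For drops used more than once daily, a surplus opening can still stand in for a missed dose on the same day: 0.21 × 0.20 = 4.2 points in one arm's mean at an assumed 20% surplus rate. Doses taken outside the monitored bottle count as missed. That may weigh more on the intervention arm, because Intervention Arm Content, item 5, allows a tailored reminder suggesting a second bottle at the workplace. Finally, device failure can be removed only where the log has captured it.
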